8.1.2. Sensitivity analysis

Two kinds of sensitivity analysis are planned to be performed for the imputation of missing values for the primary safety endpoints. Sensitivity analysis will be performed if the main analysis results show significant effect.

Extreme cases analysis:

In case a subject withdraws from study prior to 6 months follow-up visit and without experiencing previously 'device/system related complication' or 'pressure sensor failure' respectively, the subject will be defined as

This document is confidential.

having experienced such an event for the 6 months analysis. Setting all missing events to 'Y' would be the only possible extreme cases value. After imputation, below analysis will be performed.

For endpoint 1:

```
proc freq data= xxx
    tables freedom (Y/N) / binomial(exact p=0.90 level = 1) ;
run;
define level = 1 'no event = no device/system related complication'
```

For endpoint 2:

```
proc freq data= xxx
    tables freedom (Y/N) / binomial(exact p=0.95 level = 1);
run;
define level = 1 'no event = no pressure sensor failure at 6 months'
```

Tipping point analysis:

If the null hypothesis is rejected for primary safety endpoint, a tipping point analysis will be conducted based on the binary response of freedom from event/with event at 6 months using similar manner as extreme cases analysis. For subjects withdraws from study prior to 6 months follow-up visit and without experiencing previously 'device/system related complication' or 'pressure sensor failure' respectively, setting all missing events to 'N', then gradually increasing the number of subjects with event at 6 months until null hypothesis is not rejected.

8.2. Secondary safety endpoints

- 1) Pressure sensor failure rate throughout the study
- 2) Frequency of serious adverse events throughout the study
- 3) Frequency of implant procedure and procedure related adverse events and serious adverse events

Both secondary endpoints will be evaluated based on the AEs information and covered by AEs outputs.

8.3. Adverse Events

All collected adverse events (AEs) will be coded using MedDRA, version 24.0, to give a preferred term and a SOC term for each event and used for the analysis.

8.3.1.1. Device deficiency (DD)

Device deficiency is collected on a separate eCRF page called 'Device deficiency'. Summary will include the number and percent of subjects experienced device deficiency, number and percent of subjects with device deficiency resulted in AE, and number and percent of subjects with potential unanticipated adverse device effect (UADE) due to device deficiency.

8.3.2. Relationship

An AE is considered related, if the relationship to study procedure is documented as 'possibly related', or 'related'.

An AE is considered device/system related complication (DSRC), if the relationship to study device is documented as 'possible related' or 'related'.

An AE is considered related to implant procedure, if the relationship to implant procedure is documented as 'possibly related' or 'related'.

Missing and/or unknown relationship will be presented as separate category, if available.

This document is confidential.

3. CONDUCTION DISTURBANCES AND ARRHYTHMIAS
4. DEATH classified as Cardiovascular (CV) death, Non-cardiovascular death or undetermined cause of death.
5. DEVICE / SYSTEM-RELATED COMPLICATION
6. HEART FAILURE (HF)
7. HEMOPTYSIS
8. MYOCARDIAL INFARCTION (MI) classified as Peri-procedural MI (≤ 72 h after the index procedure) or Spontaneous MI (> 72 h after the index procedure)
9. PRESSURE SENSOR FAILURE
10. PULMONARY EMBOLISM
11. PULMONARY OCCLUSION
12. RENAL DYSFUNCTION classified as Acute renal dysfunction or Chronic renal dysfunction
13. STROKE (Non-Fatal) AND TRANS ISCHEMIC ATTACK (TIA) classified as Stroke or TIA
STROKE CLASSIFICATION as Ischemic, Hemorrhagic or undetermined
STROKE DEFINITION as Disabling stroke or Non-disabling stroke
14. VASCULAR ACCESS SITE AND ACCESS-RELATED COMPLICATIONS classified as Major vascular complications or Minor vascular complications
15. VESSEL TRAUMA classified as Blunt injury or Penetrating injury
16. OTHER <specify>

All SAEs and some selected AEs will be sent for adjudication.

8.3.4. Presentation

Tables will be presented as listed below.

- An overall summary of the number and percentage of subjects reporting AEs, serious AEs, study procedure related AEs, serious study procedure related AEs, AEs leading to withdrawal and AEs leading to death, DSRC, Unanticipated Adverse Device Effect (UADE), implant procedure related AEs, serious implant procedure related AEs, and subjects who died.
- Predefined AEs by category
- AEs, overall and by SOC and preferred term
- Serious AEs, overall and by SOC and preferred term
- Serious AEs, overall and by preferred term
- Serious AEs by Seriousness Criteria
- Serious predefined AEs by category

This document is confidential.

- Study procedure related AEs, overall and by SOC and preferred term
- Serious study procedure related AEs, overall and by SOC and preferred term
- Implant procedure related AEs, overall and by SOC and preferred term
- Serious implant procedure related AEs, overall and by SOC and preferred term
- Study procedure related AEs by procedure type
- AEs by maximum severity, overall and by SOC and preferred term
- AEs by maximum relationship to implant procedure, overall and by SOC and preferred term
- DSRC, overall and by SOC and preferred term
- DSRC by maximum severity, overall and by SOC and preferred term
- DSRC, by devices
- UADE, overall and by SOC and preferred term
- UADE by maximum severity, overall and by SOC and preferred term
- UADE, by devices
- Implant procedure related AEs, overall and by SOC and preferred term
- Predefined AEs by relationships to device and study procedure from CEC adjudication results
- AEs leading to study withdrawal, overall and by SOC and preferred term
- Device deficiency will be presented as described in Section [8.3.1.1](#)
- AEs, overall and by SOC and preferred term will be done for subjects with predefined AE category 'Pressure Sensor Failure'.
- anticipated AEs, overall and by SOC and preferred term
- anticipated AEs by maximum severity, overall and by SOC and preferred term
- anticipated AEs by maximum relationship to implant procedure, overall and by SOC and preferred term
- unanticipated AEs, overall and by SOC and preferred term
- unanticipated AEs by maximum severity, overall and by SOC and preferred term

This document is confidential.

- unanticipated AEs by maximum relationship to implant procedure, overall and by SOC and preferred term
- Other serious adverse events (AE) CEC adjudicated by system organ class and preferred term

Listings will be provided for all AEs, UADEs, DSRC, SAEs, anticipated AEs, unanticipated AEs, deaths, AEs leading to study withdrawal and predefined AEs by category. All collected data will be presented as available.

8.4. Laboratory Evaluations

All laboratory analyses will be performed by the local laboratory using standard assay methods. Laboratory evaluation is assessed at the study visits described in [Appendix 1: Time and Event Schedule](#) and includes chemistry, hematology, coagulation, Serum NT-pro BNP, and urinalysis with the following parameters:

Chemistry

• Sodium• Potassium• Creatinine• Total bilirubin• Blood urea nitrogen (BUN)• Urea• Total protein• Albumin• CRP• Aspartate aminotransferase (SGOT/AST)• Alanine aminotransferase (SGPT/ALT)• Cholesterol• Uric acid
Hematology

• Hemoglobin• Hematocrit• Leukocytes• Platelets• Lymphocytes
Coagulation

• INR (if indicated)• aPTT
NT-pro BNP

• NT-pro BNP
Urinalysis

• pH• Protein• Glucose• Ketones• Occult blood• RBC• WBC• Urobilinogen

This document is confidential.

• Bilirubin• Specific gravity• Nitrite
Pregnancy test

• Urine pregnancy test

All laboratory results, including abnormal ranges, will be converted to the International System (SI) units, where applicable.

Summary tables consisting of normal, abnormal clinically significant (CS) and abnormal not clinically significant (NCS) for each parameter, by visit, will be provided. If a parameter has a missing value the result will be included in the summary table as missing.

All data will be included in data listings.

Pregnancy test data will be listed only.

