8.1.9 Clinical Laboratory Tests

Blood samples will be obtained for local clinical laboratory tests (hematology and serum chemistry) at Screening, Month 6, 12, 24 and Year 3, 4 and 5. Additionally, urine samples will be obtained for testing, including pregnancy tests for females at Screening. Appropriate accreditation for all laboratories as well as the reference ranges for each of the laboratory parameters measured with a description of the methods to be used in the study must be provided to Endotronix prior to initiation of the study. Changes in the reference ranges or in the methodology during the trial are to be communicated to Endotronix or representative.

Hematology	Biochemistry		Urinalysis (Screening only)
Hemoglobin	NT-pro BNP*	CRP	Glucose
Hematocrit	Sodium	SGOT (AST)	Protein
Leucocytes	Potassium	SGPT (ALT)	Specific gravity
Platelets	Creatinine	Cholesterol	pH
Lymphocytes	Total Bilirubin	Uric Acid	Ketones
aPTT**	Blood Urea Nitrogen (BUN)/ Urea		Bilirubin
INR**	Total Protein		Urobilinogen
	Albumin		Nitrite
* also captured at Month 1, 3 and 18 ** if indicated			Blood
			Leukocytes
			Urine Pregnancy Test (females)

The results of laboratory tests will be returned to the investigator, who is responsible for filing and reviewing these results together with the data in the eCRF. The investigator is responsible for transcribing laboratory results to the eCRF. The investigator will maintain a copy of the laboratory accreditation and the reference ranges for each laboratory used.

The total amount of blood per subject for laboratory tests will be approximately 100 mL.

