Regular review of the patient’s data will allow proactive heart failure management. It is assumed that post sensor implant, more intense HF management is needed to optimize the patient’s HF treatment for a period of 1-3 months, as the patient is treated to target pressures per the guidelines in Appendix 14.5 and GDMT. Data displayed at the myCordella™ PMP will enable clinicians to effectively adjust medication dosages (e.g., drug titration) during this “optimization” period. In the following “stabilization” phase, the clinician will be able to quickly assess the patient daily health status via the myCordella™ PMP and take action as needed. As it is the nature of this particular disease, even under optimal treatment, HF patients are likely to worsen again over time. Regular review of the patient PAP trends, in addition to other data provided by the Cordella System, will allow the clinician to proactively treat the patient before full decompensation and hospitalization.

When worsening occurs, the patient will undergo again the “optimization” phase, followed by the “stabilization” phase as per the guidelines in Appendix 14.5.

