14.5 Guidelines for managing HF using Pulmonary Artery Pressures

These guidelines are required for clinicians for managing HF to allow for proactive heart failure management, if clinically tolerated by patient. It is **mandatory** to use them for all patients in Cohort #2 and Cohort #3 after the implant of the Cordella PA Sensor and for subjects in Cohort #1 as soon they have been unblinded.

Deviations from the Treatment Guidelines have to be justified.

In addition, Data and Reminders will be provided by the myCordella™ PMP to support the clinician and team to facilitate following these guidelines.

Cordella PA Sensor Treatment Guidelines for PROACTIVE-HF

¹ Thiazides: If GFR <30, use Metolazone 5 mg or Diuril 500 mg; If GFR >30, use Metolazone 2.5 or Diuril 250 mg

² ARNI indicated only for HF_rEF

Clinicians always have the ability and responsibility to overrule these Treatment Guidelines if clinically indicated.

The Clinician may override the suggested Treatment Guidelines based on clinical judgement. A note entry in Patient Management Portal during acknowledgement is required in this event to avoid a protocol deviation.

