14.6 Adverse Event Definitions

Adverse event definitions continue to evolve. The adverse event definitions below may be revised according to the published adverse event definitions as determined by following references.

References:

Kappetein et al. Updated standardized endpoint definitions for transcatheter aortic valve implantation: The Valve Academic Research Consortium-2 consensus document, *European Heart Journal* (2012) 33, 2403-2418

Rao SV et al. Standardized reporting of bleeding complications for clinical investigations in acute coronary syndromes: a proposal from the Academic Bleeding Consensus (ABC) multidisciplinary working group. *Am Heart J.* 2009;158:881–886.e1.

Hicks et al. 2014 ACC/ AHA Key Data Elements and Definitions for Cardio Vascular Endpoint Events in Clinical Trials
JACC VOL. 66, NO. 4, 2015 July 28, 2015 : 403 – 69438

ACUTE KIDNEY INJURY (AKIN CLASSIFICATION ^a)

Stage 1: Increase in serum creatinine to 150–199% (1.5–1.99 × increase compared with baseline) OR increase of ≥0.3 mg/dl (≥26.4 mmol/l) OR Urine output <0.5 ml/kg/h for >6 but <12 h.

Stage 2: Increase in serum creatinine to 200–299% (2.0–2.99 × increase compared with baseline) OR Urine output <0.5 ml/kg/h for >12 but <24 h

Stage 3^b: Increase in serum creatinine to ≥300% (>3 × increase compared with baseline) OR serum creatinine of ≥4.0 mg/dl (≥354 mmol/l) with an acute increase of at least 0.5 mg/dl (44 mmol/l) OR Urine output <0.3 ml/kg/h for ≥24 h OR Anuria for ≥12 h

The increase in creatinine must occur within 48 h.

^a Metha et al; Acute Kidney Injury N. Acute Kidney Injury Network: Report of an initiative to improve outcomes in acute kidney injury. *Crit Care* 2007;11: R31.

^b Patients receiving renal replacement therapy are considered to meet Stage 3 criteria irrespective of other criteria.

BLEEDING

Life-threatening or disabling bleeding

- Fatal bleeding (BARC type 5)

OR

- Bleeding in a critical organ, such as intracranial, intraspinal, intraocular, or pericardial necessitating peri cardiocentesis, or intramuscular with compartment syndrome (BARC type 3b and 3c).

OR

Bleeding causing hypovolemic shock or severe hypotension requiring vasopressors or surgery (BARC type 3b).

OR

- Overt source of bleeding with drop in hemoglobin ≥ 5 g/dl or whole blood or packed red blood cells (RBCs) transfusion ≥ 4 units ^a (BARC type 3b).

Major bleeding (BARC type 3a)

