	14.3.1.29.2	Unanticipated Adverse Events by System Organ Class and Preferred Term and Maximum Severity	Cohort #1 Population
	14.3.1.30.1	Unanticipated Adverse Events by System Organ Class and Preferred Term and Maximum Relationship to Implant Procedure	ITT Population
	14.3.1.30.2	Unanticipated Adverse Events by System Organ Class and Preferred Term and Maximum Relationship to Implant Procedure	Cohort #1 Population
	14.3.1.31.1	Other serious adverse events (AE) CEC adjudicated by system organ class and preferred term	ITT Population
	14.3.1.31.2	Other serious adverse events (AE) CEC adjudicated by system organ class and preferred term	Cohort #1 Population
14.3.2		Listings of Deaths, Other Serious and Significant Adverse Events	
	14.3.2.1.1	Deaths from Adverse Event Page, Listing	Enrolled Population
	14.3.2.1.2	Deaths from Study Completion Page, Listing	Enrolled Population
	14.3.2.1.3	Deaths from Adverse Event Page, Listing	Cohort #1 Population
	14.3.2.1.4	Deaths from Study Completion Page, Listing	Cohort #1 Population
	14.3.2.2	Serious Adverse Events, Listing	Enrolled Population

This document is confidential.

Header	Table Number	Name	Analysis Set
	14.3.2.3	Unanticipated Adverse Device Effects, Listing	Enrolled Population
	14.3.2.4	Adverse Events Leading to Study Withdrawal, Listing	Enrolled Population
	14.3.2.5	Serious Adverse Events, Listing	Cohort #1 Population
	14.3.2.6	Unanticipated Adverse Device Effects, Listing	Cohort #1 Population
	14.3.2.7	Adverse Events Leading to Study Withdrawal, Listing	Cohort #1 Population
14.3.3	Not to be used for any Tables	Narratives of Deaths, Other Serious and Certain Other Significant Adverse Events	
14.3.4		Abnormal Laboratory Value (each subject)	
14.3.4.1		Clinical Laboratory Data	
14.3.4.1.1		Hematology Data	
	14.3.4.1.1.1	Hematology: Proportion of Abnormal Results by Visit	ITT Population
	14.3.4.1.1.2	Hematology: Abnormal Results, Listing	ITT Population
	14.3.4.1.1.3	Hematology: Proportion of Abnormal Results by Visit	Cohort #1 Population
	14.3.4.1.1.4	Hematology: Abnormal Results, Listing	Cohort #1 Population
14.3.4.1.2		Chemistry Data	
	14.3.4.1.2.1	Chemistry: Proportion of Abnormal Results by Visit	ITT Population
	14.3.4.1.2.2	Chemistry: Abnormal Results, Listing	ITT Population
	14.3.4.1.2.3	Chemistry: Proportion of Abnormal Results by Visit	Cohort #1 Population
	14.3.4.1.2.4	Chemistry: Abnormal Results, Listing	Cohort #1 Population
14.3.4.1.3		Urinalysis Data	

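### Creatinine and potassium are tabulated only as normal or abnormal, so the size of renal change is never summarised; the AKI creatinine cut-offs are also about 1000-fold too high in SI units as printed

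*SAP*

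**What the plan says.** **Tabulation.** SAP 8.4 describes the laboratory output as follows: "Summary tables consisting of normal, abnormal clinically significant (CS) and abnormal not clinically significant (NCS) for each parameter, by visit, will be provided". The index of tables (SAP section 14) agrees. The only chemistry summary, produced for the ITT and Cohort #1 populations, is titled "Chemistry: Proportion of Abnormal Results by Visit"; the other chemistry outputs are listings. On listings SAP 8.4 says: "All data will be included in data listings". The same section converts laboratory results to SI units.

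**Renal adverse events.** SAP 8.3.3 takes two predefined renal categories from Protocol 14.6: acute kidney injury (AKI), by stage, and renal dysfunction, acute or chronic. The Stage 1 absolute criterion for AKI reads "increase of ≥0.3 mg/dl (≥26.4 mmol/l", and the definition adds: "The increase in creatinine must occur within 48 h". Stage 3 prints 4.0 mg/dl as 354 mmol/l and 0.5 mg/dl as 44 mmol/l.

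**Schedule.** Protocol 8.1.9 sets the local blood tests as "hematology and serum chemistry) at Screening, Month 6, 12, 24 and Year 3, 4 and 5". Months 1, 3 and 18 add NT-proBNP only. Protocol 8.1.20 expects more intense management after implant "for a period of 1-3 months, as the patient is treated to target pressures". A footnote to the treatment guideline in Protocol 14.5 begins "Thiazides: If GFR <30".

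**The concern.** The trial has a single arm, so a subject's own baseline is the only reference inside the study for a laboratory value. A table of normal and abnormal counts discards that reference. A subject whose creatinine is abnormal at baseline stays abnormal however far it rises. The only movement the table can show is a change in the investigator's grade between not clinically significant and clinically significant. Even that appears as marginal counts per visit, not as a within-subject shift.

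Subjects with GFR of 25 ml/min or more may enter, so reduced renal function at baseline is allowed. The guideline footnote depends on GFR, so the plan itself treats renal function as relevant to the titration. At stake is whether the report can say by how much creatinine and potassium changed after implant.

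The unit error matters because SAP 8.3.3 stages AKI by a definition whose absolute SI cut-offs are impossible as printed, in a plan that converts results to SI.

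**Working it through.** **1. Laboratory output against the plan's own rule**

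- Protocol 10.7 and the opening of SAP section 8: quantitative safety outcomes get n, mean, SD, median, minimum and maximum.
- SAP 8.5, vital signs: absolute value and change from baseline.
- SAP 8.6, ECG: shifts from baseline in the overall evaluation.
- SAP 8.4, chemistry: three categories by visit, with no value, change or shift.
- SAP section 10, changes from the protocol: silent on this.

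Chemistry thus falls short of the stated rule and gets less than vital signs or ECG.

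**2. Do the predefined renal categories fill the gap?**

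Take a gradual rise from 1.6 to 3.2 mg/dl (illustrative values, not from the documents). The ratio is 3.2 / 1.6 = 2.0 and the rise is 3.2 − 1.6 = 1.6 mg/dl. Against Protocol 14.6:

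- AKI: 200% of baseline is the size required for Stage 2, but the rise must occur within 48 h. A gradual rise does not qualify.
- Acute renal dysfunction: more than 3 times baseline (3 × 1.6 = 4.8) or more than 5 mg/dl. The value 3.2 is below both.
- Chronic renal dysfunction: a rise of at least 2 mg/dl. The rise is 1.6.

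No creatinine criterion is met. More generally, in a doubling the rise equals the baseline, so the chronic criterion fails for any baseline below 2.0 mg/dl. The end value is then below 4.0, short of 5 mg/dl, and a doubling never exceeds 3 times baseline. The conclusion therefore holds for a gradual doubling from any baseline below 2.0 mg/dl. Dialysis or low urine output would be caught by other criteria.

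**3. Units in the AKI definition**

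The molar mass of creatinine is taken as 113.12 g/mol (a physical constant, not in the documents). Formula: micromol/l = mg/dl × 10 / 113.12 × 1000.

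| mg/dl | Printed | Converted, micromol/l | Converted, mmol/l | Printed mmol/l ÷ converted mmol/l |
|---|---|---|---|---|
| 0.3 | 26.4 mmol/l | 26.52 | 0.0265 | 996 |
| 4.0 | 354 mmol/l | 353.61 | 0.3536 | 1001 |
| 0.5 | 44 mmol/l | 44.20 | 0.0442 | 996 |

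The printed numbers reproduce within 0.5% as micromol/l and do not reproduce as mmol/l. A check that needs no assumed constant uses the printed pairs, whose ratios are 26.4 / 0.3 = 88.0, 354 / 4.0 = 88.5 and 44 / 0.5 = 88.0. Read as mmol/l, these imply a molar mass of about 0.113 g/mol, which is impossible; read as micromol/l, about 113 g/mol. Taken literally, 26.4 mmol/l would be about 299 mg/dl.

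**4. Timing of routine chemistry**

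The Month 6 visit is at 180 ± 14 days, so the first routine post-implant draw falls between 180 − 14 = 166 and 180 + 14 = 194 days. The optimisation period in Protocol 8.1.20 is 1-3 months. Two conditional draws exist: a pre-implant repeat, including creatinine, potassium and GFR, if the implant is more than 30 days after Visit 1 (Protocol 8.3.1), and chemistry at early termination (8.3.9). Only the second can fall between implant and Month 6. Routine draws cannot by themselves show a rise within 48 h, so finding AKI on the creatinine criteria depends on unscheduled clinical tests.

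**The case against.** The strongest reply is that renal safety is already covered. AKI and renal dysfunction are predefined, tabulated overall, by seriousness, by sex and by ejection fraction, and tabulated again from CEC adjudication; every laboratory value is listed. That stands. A reader might infer that renal safety cannot be read from the plan at all, and the documents do not support that. What is missing is a summary of the size of change.

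Other strong readings also fail:

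- *The example would leave no trace.* It could move a subject from NCS to CS if the investigator regrades it, or be reported as another adverse event.
- *Many subjects will start with abnormal creatinine.* The documents give an exclusion floor, not a proportion.
- *AKI could never be recorded in SI units.* The percentage-rise and urine-output criteria carry no creatinine unit, Stage 2 has no absolute cut-off, and the correct mg/dl figure stands first each time. Renal dysfunction is defined in mg/dl only. The SAP gives no rule deriving AKI from laboratory data.
- *The 10% anticipated rate of renal insufficiency or failure shows a cost of titration.* That entry in Protocol 9.1.4 cites a study of contrast-induced nephropathy and acute renal failure after emergent catheterisation, a procedural risk.
- *The schedule and the guideline contradict each other.* I have only the footnotes of the treatment chart in Protocol 14.5, not the chart, so a contradiction is not shown. Protocol 7.3 continues ordinary medical management throughout, and clinical tests outside the study schedule are not ruled out.

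**Conclusion.** The point holds as a reporting gap and a unit error. SAP 8.4 and its chemistry tables do not deliver the descriptive statistics that Protocol 10.7 and SAP section 8 promise, and SAP section 10 does not declare the departure. A gradual doubling of creatinine from a baseline below 2.0 mg/dl meets no creatinine criterion in the predefined renal categories and has no summary table to show it. The three SI cut-offs in the AKI definition are too high by a factor of 996 to 1001 as printed.

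This rests on the molar mass of creatinine, although the printed pairs alone point the same way, and on the printed page really showing mmol/l; a misread micro sign is possible and should be checked. The mg/dl, percentage-rise and urine-output criteria are unaffected. On timing, the documents support only this: routine chemistry after implant starts at Month 6, after the stated optimisation period, apart from early termination.

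**What to change.** 1. **SAP 8.4 and the table index.** Add observed value, change from baseline, and baseline-to-worst-post-baseline shift tables for creatinine (with derived eGFR where possible) and potassium. Baseline is already defined in SAP 5.2. State whether unscheduled and early-termination values count towards the worst value, because SAP 5.1 otherwise uses the planned visit. Cost: a few tables on data already collected.
2. **Protocol 14.6 and SAP 8.3.3.** After checking the printed page, correct mmol/l to micromol/l in the three creatinine criteria. In SAP 8.3.3 read Stage 3b as Stage 3; the b is a footnote mark in Protocol 14.6. Cost: wording only.
3. **Protocol 8.1.9, 8.1.20, 14.1 and 14.5.** The sponsor should reconcile the chemistry schedule with the 1-3 month optimisation period and the GFR-dependent footnote. No sampling schedule or clinical rule is proposed here. Cost: a clarification.
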